**NOTES :**

- Please refer to [Appendix 10](#): List of Data Displays which details the population to be used for each display being generated.
- If a participant is inadvertently given both study treatments they will be analysed according to the treatment that they received the more frequently.

#### 4.1. Protocol Deviations

All important protocol deviations (including deviations related to study inclusion/exclusion criteria, conduct of the trial, patient management or patient assessment) will be summarised and listed.

Protocol deviations will be tracked by the study team throughout the conduct of the study in accordance with the Protocol Deviation Management Plan [21-Aug-2017 (Version 1) or later].

- Data will be reviewed prior to unblinding and freezing the database to ensure all important deviations are captured and categorised on the protocol deviations dataset.
- This dataset will be the basis for the summaries and listings of protocol deviations.

A separate summary and listing of all inclusion/exclusion criteria deviations will also be provided. This summary will be based on data as recorded on the inclusion/exclusion page of the eCRF.

Note: Inclusion and exclusion criteria deviations are always reported as important.

## 5. CONSIDERATIONS FOR DATA ANALYSES AND DATA HANDLING CONVENTIONS

### 5.1. Study Treatment & Sub-group Display Descriptors

Treatment Group Descriptions			
RandAll NG		Data Displays for Reporting	
Code	Description	Description	Order 
G	GSK3772847 10 mg/kg	GSK3772847	2
P	Placebo	Placebo	1

**NOTES:**

- Order represents treatments being presented in TFL, as appropriate.

Treatment comparisons will be displayed as follows using the descriptors as specified:

- GSK3772847 vs Placebo

There were four strata used for the randomisation depending on the participants baseline blood eosinophil count and whether they consented to the sputum sub-study:

- Sputum sub-study and screening blood eosinophils < 150 cells/ $\mu$ L
- Sputum sub-study and screening blood eosinophils  $\geq$ 150 cells/ $\mu$ L
- Not sputum sub-study and screening blood eosinophils < 150 cells/ $\mu$ L
- Not sputum sub-study and screening blood eosinophils  $\geq$ 150 cells/ $\mu$ L

Displays will be presented by combining data across all four strata to give the overall estimate of GSK3772847 versus placebo.

Sputum sub-study will not be accounted for within the statistical analysis as the sputum sub-study strata was for monitoring recruitment only.

An additional exploratory analysis using fractional polynomials has been added to further investigate the relationship between loss of control and screening eosinophils and summary statistics on eosinophils will also be provided.

## 5.2. Baseline Definitions

For all endpoints (except as noted in baseline definitions) the baseline value will be the latest pre-dose assessment with a non-missing value, including those from unscheduled visits.

Parameter	Study Assessments Considered As Baseline			Baseline Used in Data Display
	Pre-Screening	Screen Run-in	Day 1 (Pre-Dose)	
Loss of Asthma Control				
Pre-bronchodilator Forced expiratory volume in 1 second (FEV 1 )		X	X	Day 1
Asthma Control Questionnaire (ACQ-5) score		X	X	Day 1
Other Patient Reported Outcomes				
St. George's Respiratory Questionnaire (SGRQ)			X	Day 1
Peak Expiratory Flow (PEF)				
Mean morning peak expiratory flow (PEF)		X	X	Run-in [1]
Mean evening peak expiratory flow (PEF)		X	X	Run-in [1]
Fractional Exhaled Nitric Oxide (FeNO)				
Fractional Exhaled Nitric Oxide (FeNO)			X	Day 1
Symptom Scores				
Mean daytime asthma symptom score		X	X	Run-in [1]
Night-time awakenings due to asthma symptoms requiring rescue medication		X	X	Run-in [1]

Parameter	Study Assessments Considered As Baseline			Baseline Used in Data Display
	Pre- Screening	Screen Run-in	Day 1 (Pre-Dose)	
Rescue Medication				
Rescue medication use		X	X	Run-in [1]
Mean number of inhalations per day over each four weeks		X	X	Run-in [1]
Safety				
Vital Signs		X	X	Day 1
12-lead Electrocardiogram (ECG) measurements		X	X	Day 1
24 hours Holter measurements		X		Screen/Run in
Clinical laboratory tests (haematology and chemistry)		X	X	Day 1
Biomarkers				
Induced sputum biomarkers			X	Day 1
Serum biomarkers			X	Day 1
Exploratory serum markers			X	Day 1

**NOTES :**

- Unless otherwise stated, the mean of replicate assessments at any given time point will be used as the value for that time point.
- [1] Mean over the last 7 days of the run-in period prior to V2. Participants must have at least 4 full days of data (morning and evening) in the last 7 days of run-in to be eligible.

**5.3. Multicentre Studies**

In this multicentre global study, enrolment will be presented by investigative site, country, and regions.

Region	Countries
North America	United States, Canada
Latin America	Mexico
Eastern Europe	Ukraine, Russian Federation
Oceania	Australia

## 5.4. Examination of Covariates, Other Strata and Subgroups

### 5.4.1. Covariates and Other Strata

The list of covariates and other strata may be used in descriptive summaries and statistical analyses, some of which may also be used for subgroup analyses. Additional covariates and other strata of clinical interest may also be considered.

Category	Covariates
Screening eosinophils	
At randomisation participants are stratified according to their screening peripheral blood eosinophil count. Screening eosinophils will be included in both primary and secondary analysis as a categorical variable (<150 cells/<math>\mu</math>L, <math>\geq</math>150 cells/<math>\mu</math>L).
 
If the analysis models are unable to converge due to low number of participants with screening blood eosinophils <150 cells/<math>\mu</math>L, then screening eosinophil will be re-categorised according to a cut point of 300 cells/<math>\mu</math>L instead i.e. <300 cells/<math>\mu</math>L and <math>\geq</math>300 cells/<math>\mu</math>L

## 5.5. Multiple Comparisons and Multiplicity

As there is a single primary treatment comparison, no adjustment is required for primary comparisons. No adjustments will be made for multiplicity for other endpoints.

## 5.6. Other Considerations for Data Analyses and Data Handling Conventions

Other considerations for data analyses and data handling conventions are outlined in the appendices:

Section	Component
12.3	Appendix 3: Assessment Windows
12.4	Appendix 4: Study Phases and Treatment Emergent Adverse Events
12.5	Appendix 5: Data Display Standards & Handling Conventions
12.6	Appendix 6: Derived and Transformed Data
12.7	Appendix 7: Reporting Standards for Missing Data
12.8	Appendix 8: Values of Potential Clinical Importance

## **6. STUDY POPULATION ANALYSES**

### **6.1. Overview of Planned Study Population Analyses**

The study population analyses will be based on the Safety Population including GCP non-compliant subjects population (SAFF\_ALL), unless specified to be on the All Subjects Enrolled (ASE) population.

Study population analyses including analyses of subject's disposition, protocol deviations, demographic and baseline characteristics, prior and concomitant medications, and exposure and treatment compliance will be based on GSK Core Data Standards. Details of the planned displays are presented in [Appendix 10: List of Data Displays](#).

### **6.2. Disposition**

The study population summary will use the All Subjects Enrolled (ASE) population and show the number of subjects overall who were enrolled, the number of screen failures and the number with each reason for screen failure. It will also show the number of subjects who were randomised and who were in the modified Intent-to-treat (Loss of Control), modified Intent-to-treat, Safety including GCP non-compliant subjects, and PK populations.

For the Safety including GCP non-compliant subjects, reasons for withdrawal summary will show the number and percentage of subjects who completed the study, who withdrew prematurely from the study and who reported each primary and sub-reason for withdrawal.

### **6.3. Medical Conditions**

The number and percentage of subjects reporting each current medical condition will be presented. This table will include a subheading of 'Cardiovascular Disorders,' which will summarise the information taken from the cardiac disorders page in the eCRF. All medical conditions must be summarised on this table regardless of frequency. This will be repeated for past medical conditions.

### **6.4. Concomitant Medications**

Non-Asthma medications will be summarised by Anatomical-Therapeutic-Chemical (ATC) level 1 and ingredient. Asthma medications will be summarised by the latest version of the Respiratory Medication Class (RMC), and will be derived for each asthma concomitant medication. Multi-ingredient medications will be presented according to their combination ATC classification rather than the classifications of the ingredients.

Asthma and non-asthma medications will be listed separately. A listing of the relationship between ATC Level 1, ingredient and verbatim text will be produced for non-asthma medications only.

## 7. EFFICACY ANALYSES

### 7.1. Primary Efficacy Analyses

#### 7.1.1. Endpoint

- Proportion of participants with loss of asthma control over Weeks 0-16
- Proportion of participants with loss of asthma control over Weeks 0-6 (Secondary)

#### 7.1.2. Summary Measure

Bayesian Method (Primary): The posterior median and 95% credible interval. In addition, the posterior probabilities that the ratio of the proportion of subjects with loss of asthma control on GSK3772847 compared with placebo is less than 1.0, 0.75, 0.7, 0.5 and 0.2 (i.e. more than a 0%, 25%, 30%, 50% and 80% reduction), and greater than 0.6 (i.e. less than a 40% reduction).

Frequentist Method (Supportive): Odds Ratio. The odds of having experienced loss of asthma control on GSK3772847 compared to the odds of having experienced loss of asthma control on placebo.

#### 7.1.3. Population of Interest

The primary efficacy analyses will be based on the modified Intent to Treat (Loss of Control) population, unless otherwise specified.

#### 7.1.4. Strategy for Intercurrent (Post-Randomisation) Events

Intercurrent Event	Primary Estimand	Secondary Estimand
Study treatment discontinuation due to an AE/SAE	Excluded from analysis	Set as loss of asthma control (i.e. worst case scenario).
Death	Excluded from analysis	Set as loss of asthma control (i.e. worst case scenario).
Prohibited/ Concomitant medications that could impact patients' asthma control	Use data as is.	Set as loss of asthma control (i.e. worst case scenario).
Non-compliance with FP/SAL, FP or study titration	Use data as is.	Set as loss of asthma control (i.e. worst case scenario).
Missing data *	Excluded from analysis	Set as loss of asthma control (i.e. worst case scenario).
Notes:		

 
• * Missing data is not an intercurrent event, however missing values will be imputed according to the estimand under investigation.
 
		

- |  |
|--|
| 
 
• If the intercurrent event occurs after loss of asthma control then all information on loss of asthma control will be used.
 
• Prohibited/ concomitant medications will be identified as protocol deviations within the prohibited/ concomitant medications category and will have text that start with “LoAC”
 
• Non-compliance FP/SAL, FP or study titration will be identified as compliance <80%, compliance ≥ 120% or protocol deviations within the other deviations related to wrong study treatment/administration/dose sub-category and will have text that starts with “TIT”
 
 |
|--|

If any of the following intercurrent events occurs, then all data will be accepted:

- Pregnancy  
Accidental unblinding

Whilst it’s possible that site staff were unable to administer study drug as they were unable to find a suitable vein, the team felt this would not be caused by the randomised study treatment and the visit would be rescheduled. Therefore, if this occurs all data will be accepted and treated as any other out of window assessment.

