**Table 1 Changes to Protocol Defined Analysis Plan**

Protocol	Reporting & Analysis Plan	
Statistical Analysis Plan	Statistical Analysis Plan	Rationale for Changes
Modified Intent to Treat population.	Modified Intent to Treat (Loss of Control), Modified Intent to Treat and Safety excluding GCP non-compliant subjects populations.	The Modified Intent to Treat (Loss of Control) was added to account for the intercurrent event when participants receive the wrong study treatment. Whilst the data from GCP non-compliant participants should not be used in the efficacy analysis, the participants were dosed with GSK3772847 or Placebo so all safety data (AEs, SAEs, ECGs etc.) should be reported.
Section 10.4.1 of the protocol describes a sensitivity analysis where data is analysed as missing and worst case (loss of control) for participants who withdraw from the study for reasons other than loss of asthma control.	A primary and secondary estimand have been defined to capture where data is analysed as missing and worst case (loss of control) for various intercurrent events where participants withdraw from the study for reasons other than loss of asthma control.	The protocol was approved before the ICH E9 addendum on estimands. The RAP is performing the same planned analysis as detailed in the Protocol however the terminology has been updated in accordance with ICH E9.
Statistical analysis would be performed for each screening eosinophil strata separately.	Bayesian analysis will include screening eosinophil strata as a covariate instead of performing split analysis models.  In addition, an exploratory analysis using fractional polynomials was added to examine the relationship between loss of control and screening eosinophils (continuous), IgE and FeNO.	Bayesian analysis will now include the same covariates as the frequentist analysis.  By modelling eosinophils as a continuous endpoint, it will provide more information on the impact of varying screening eosinophil levels on the treatment effect. It will also provide additional information on the role of IgE and FeNO on loss of asthma control.

Protocol	Reporting & Analysis Plan	
Statistical Analysis Plan	Statistical Analysis Plan	Rationale for Changes

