## 2.4. Study Design

Overview of Study Design and Key Features	
 
The diagram illustrates the study design timeline from Week 0 to Week 28. It is divided into a Treatment Phase (Weeks 0-12) and a Follow Up Phase (Weeks 16-28). In the Treatment Phase, participants receive a double-blind study treatment every 4 weeks, either GSK3772847 or Placebo, at Weeks 0, 4, 8, and 12. Simultaneously, background therapy is reduced from LABA, Sal, and ICS at Week 0 to FP 500 BID at Week 2, and then further reduced to FP 250 BID, FP 100 BID, and FP 50 BID by Week 10. In the Follow Up Phase, participants receive LABA and ICS from Week 16 to Week 28. Visits are labeled V0 through V14, with an ETP Visit at Week 11.
	
Design Features	
 
The study is a Phase IIa, multicenter, randomised, placebo-controlled, double-blind, stratified, parallel group study.
 

Dosing	
 
Participants will have a two-week Run-in period in which they take a background therapy of fluticasone propionate (FP)/salmeterol 500/50 mcg BID.
 
Following run-in they will be randomised to receive four doses of either GSK3772847 or Placebo intravenously (Week 0, 4, 8 and 12) whilst initially still receiving background FP/Salmeterol 500/50 mcg BID.
 
At Week 2 background therapy will be changed to FP 500 mcg BID only. This will then be reduced by approximately 50 % every two weeks until complete FP discontinuation at Week 10.
 

Treatment Assignment	
 
Participants will be randomised in a 1:1 ratio to receive four doses of either GSK3772847 or Placebo administered intravenously every 4 weeks.
 
Randomisation will be stratified based on participants' baseline peripheral blood eosinophil count which is measured at screening (<150 cells/<math>\mu</math>L, <math>\geq</math>150 cells/<math>\mu</math>L), Randomisation will also be stratified according to whether participants consent to the sputum sub study.
 

Overview of Study Design and Key Features	

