## 2.5. Statistical Hypotheses

The primary null hypothesis ( $H_0$ ) for this study is that the ratio of the proportions of subjects with loss of asthma control from randomisation to Week 16 between GSK3772847 and placebo is unity.

$$H_0: \frac{\text{Proportion with loss of asthma control at Week 16 on GSK3772847}}{\text{Proportion with loss of asthma control at Week 16 on Placebo}} = 1$$

The alternative hypothesis ( $H_1$ ) for this study is that the ratio of the proportions of subjects with loss of asthma control from randomisation to Week 16 between GSK3772847 and placebo is not unity.

$$H_1: \frac{\text{Proportion with loss of asthma control at Week 16 on GSK3772847}}{\text{Proportion with loss of asthma control at Week 16 on Placebo}} \neq 1$$

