## 2.6. Sample Size Calculations

With 70 evaluable participants per arm and assuming the true proportion with loss of control on placebo is 44%, the smallest observed difference that would lead to rejection of the null hypothesis (minimum detectable effect) is 36% corresponding to a proportion with loss of control on GSK3772847 of 28%.

As detailed in Section 2.1, there was a typographical error in the protocol which meant that minimum detectable effect was incorrectly reported as 31%, this has been corrected above.

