### Model Results Presentation

Bayesian Method (Primary):

- The proportions of participants experience loss of asthma control on GSK3772847, Placebo and the ratio of GSK3772847/Placebo will be presented along with their 95% credible interval.

Frequentist Method (Supportive):

- The proportion of participants experiencing loss of asthma control on GSK3772847, Placebo and the odds ratio will be presented along with the 95% confidence intervals and p-value. This will be presented for all participants combined.

Fractional Polynomials (Exploratory Analysis):

- A plot of the relationship between the probability of experiencing loss of control on each treatment as well as the odds ratio versus continuous eosinophils will be produced.

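### Counting every affected participant as a loss of control in both arms is a composite rule, not a worst case for the GSK3772847/placebo ratio, and no planned analysis bounds the effect of missing outcomes

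*SAP*

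**What the plan says.** The document binds two versions of the RAP. This point concerns the amended one, which comes first.

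- **Section 7.1.4, primary estimand.** Participants who discontinue for an AE/SAE, who die or whose outcome is missing are "Excluded from analysis". Prohibited medication and non-compliance leave the observed data unchanged.
- **Section 7.1.4, secondary estimand.** All five rows read "Set as loss of asthma control (i.e. worst case scenario"). Nothing distinguishes the arms.
- **Sections 7.1.2 and 7.1.5.1.** The primary summary is Bayesian: the posterior of the GSK3772847/placebo ratio of proportions, where values below 1 favour the drug.
- **Section 7.2.3.** In explaining why time to loss of control needs both estimands, the SAP reasons that missingness depends on treatment and could bias the estimates.
- **Section 12.10.5, Tables 2.4 to 2.13.** Loss of control is analysed under these two estimands only. No arm-specific, delta or tipping-point analysis is listed.

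Table 1 in Section 2.1 gives the origin of the pair: the protocol "describes a sensitivity analysis where data is analysed as missing and worst case (loss of control") for those who withdraw for other reasons. That entry only describes the protocol and is background here.

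**The concern.** A worst-case analysis is normally read as a limit: if the result survives it, the missing data cannot overturn the result. For a single-arm proportion, setting every missing outcome to failure is such a limit. For a ratio of two arms it is not, because failures added to the placebo arm enlarge the denominator and offset those added to the drug arm.

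Two consequences follow. With balanced missingness, the planned check moves the ratio only part of the way to the limit. With missingness sufficiently heavier on placebo, the check moves the ratio towards the drug and looks better than the analysis it is meant to test. The SAP itself expects missingness to depend on treatment, so unequal missingness is a case this check should be able to handle. At stake is how the robustness statement in the study report would be understood.

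**Working it through.** **Design inputs.** Section 2.6: "With 70 evaluable participants per arm and assuming the true proportion with loss of control on placebo is 44"%, and the "minimum detectable effect) is 36% corresponding to a proportion with loss of control on GSK3772847 of 28"%. Section 2.4: "Participants will be randomised in a 1:1 ratio". Section 2.5 is two-sided (the ratio "between GSK3772847 and placebo is not unity"). Alpha is not stated; two-sided 5% is assumed because results "will be presented along with the 95% confidence intervals and p-value".

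**Reproducing the SAP's figure.** (0.44 − 0.28)/0.44 = 36.4%. Pooled proportion 0.36; SE = √(0.36 × 0.64 × 2/70) = 0.0811; z = 0.16/0.0811 = 1.97, just above 1.96. The stated 36% and 28% hold.

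**Three treatments of missing outcomes.** With 70 per arm, let x be observed losses and m missing outcomes (subscript g for GSK3772847, p for placebo):

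- Primary: [x_g/(70 − m_g)] / [x_p/(70 − m_p)]
- SAP secondary: (x_g + m_g)/(x_p + m_p)
- Drug-conservative limit (missing = loss on GSK3772847, no loss on placebo): (x_g + m_g)/x_p

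**When the SAP rule favours the drug.** Let r be the observed rate among those with an outcome and s the missing share. The imputed rate is r + s(1 − r) = r[1 + s(1 − r)/r]. The ratio therefore falls below its primary value exactly when s_p(1 − r_p)/r_p > s_g(1 − r_g)/r_g, that is, when

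s_p/s_g > [r_p/(1 − r_p)] / [r_g/(1 − r_g)] = 1/OR.

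At 28% v 44% this is (0.44/0.56)/(0.28/0.72) = 0.786/0.389 = 2.02. With no drug effect it is 1.

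**Results.** All counts are assumed and unadjusted for eosinophil stratum. Each pair is GSK3772847 then placebo.

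| Case | Losses / with outcome | Missing | s_p/s_g v 1/OR | Primary | SAP rule | Limit |
|---|---|---|---|---|---|---|
| A | 20/63, 31/63 | 7, 7 | 1 v 2.08 | 0.645 | 27/38 = 0.711 | 27/31 = 0.871 |
| B | 22/67, 27/58 | 3, 12 | 4 v 1.78 | 0.705 | 25/39 = 0.641 | 25/27 = 0.926 |
| C | 20/63, 31/60 | 7, 10 | 1.43 v 2.30 | 0.614 | 27/41 = 0.659 | 27/31 = 0.871 |
| D | 20/63, 31/56 | 7, 14 | 2 v 2.67 | 0.573 | 27/45 = 0.600 | 27/31 = 0.871 |
| E | 18/66, 26/60 | 4, 10 | 2.5 v 2.04 | 0.629 | 22/36 = 0.611 | 22/26 = 0.846 |
| F | 17/60, 29/66 | 10, 4 | 0.4 v 1.98 | 0.645 | 27/33 = 0.818 | 27/29 = 0.931 |
| G | 28/63, 25/56 | 7, 14 | 2 v 1.01 | 0.996 | 35/39 = 0.897 | 35/25 = 1.400 |

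The SAP rule lies short of the limit in every row. It moves towards the drug only in B, E and G, the three rows that exceed 1/OR.

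**On the posterior scale** (near-flat independent beta posteriors, no stratum term):

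- Case E: P(ratio<1) goes from 0.972 to 0.992 under the SAP rule, and is 0.763 at the limit. P(ratio<0.7) goes from 0.67 to 0.75 under the SAP rule.
- Case G, where the observed rates are nearly equal: P(ratio<1) goes from 0.51 to 0.75 under the SAP rule.

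The table covers missing outcomes only. The SAP rule also overwrites observed outcomes for prohibited medication and non-compliance, so an excess of those events on placebo would push the same way.

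**The case against.** Several points on the other side stand.

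- **Event = failure is a legitimate composite estimand.** In Section 7.1.4 the phrase can be read as describing each participant's value. Section 7.2.3 describes the same rule as setting missing data to non-response. A reader might infer that the SAP claims its two estimands bracket the effect; it nowhere says so.
- **More leavers on placebo is not enough.** A reader might infer that any excess on placebo flatters the drug. Cases C and D show otherwise, and with heavier loss on the drug the rule is clearly conservative (case F).
- **The drug-conservative limit is not a likely truth.** If placebo participants leave because their asthma worsens as ICS/LABA is withdrawn, counting them as losses is close to right. The endpoint also captures many such exits directly.
- **Significance is the wrong yardstick.** In case B the pooled z-test goes from p = 0.12 to p = 0.018, and a reader might infer that a failed trial could be turned into a positive one. The primary analysis is Bayesian with no stated threshold, the frequentist model is supportive and stratum-adjusted, and the study is Phase IIa.
- **Some mitigation exists.** Intercurrent events are tabulated and listed (Table 2.3, Listing 35), so an imbalance would be visible. The primary Kaplan-Meier analysis (Section 7.2.4.1) uses leavers' partial follow-up by censoring them. It does this under a single assumption, however, and its secondary version again counts leavers as events in both arms.

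None of this makes the rule a bound on the ratio, or supplies one elsewhere.

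**Conclusion.** The point holds in a limited form. The secondary estimand is acceptable as a composite strategy, but the worst-case label is wrong for a between-arm ratio. Under balanced missingness of 7 per arm it gives 0.711 where the limit is 0.871. It favours the drug only when the placebo-to-drug ratio of missing shares exceeds 1/OR: about 2 at the SAP's design rates, and 1 if the drug has no effect. The primary proportion endpoint has no other planned missing-data analysis.

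The SAP gives no dropout figure, so every missing count above (up to 14 of 70, or 20%, per arm) is an illustration and not a forecast. The documents do not show that placebo will lose more participants, that the secondary result will favour the drug, or that the primary analysis is invalid. The 1/OR condition itself is algebra and does not depend on the chosen counts.

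**What to change.** 1. In Section 7.1.4, replace the worst-case wording with a composite (event = failure) description, and use that term for the secondary estimand in the report.
2. Add one sensitivity table for loss of control over Weeks 0-16: a two-way tipping-point grid over the number of losses assumed among participants with missing outcomes in each arm, showing the ratio and P(ratio<1) in each cell. State whether AE/SAE discontinuations and deaths, which the primary estimand also drops, are included. Mark the cell with all losses on GSK3772847 and none on placebo as the extreme corner, not as a plausible scenario.

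The cost is a wording change and a little more programming on data already collected. The drawback is that the stated robustness may look less favourable.
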